Study Type: Interventional

Actual Enrollment: 205 participants

Allocation: Randomized

Intervention Model: Parallel Assignment

Masking: Double (Participant, Investigator)

Primary Purpose: Treatment

Official Title: Effects of Carnitine Supplementation on Exercise-Induced Muscle Damage: A Randomized Controlled Trial

Actual Study Start Date: May 9, 2025

Actual Primary Completion Date: May 15, 2025

Actual Study Completion Date: June 5, 2025

METHOD

Participants

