This randomized, double-blind, placebo-controlled study was conducted to investigate the effects of L-carnitine supplementation on markers of muscle damage and delayed onset muscle soreness following high-intensity interval training in trained athletes. The study was reported in accordance with CONSORT guidelines for randomized controlled trials. The exercise protocol, anthropometric measurements (and supplement protocol of the study were carried out by the researchers at the Exercise Laboratory of Istanbul Sabahattin Zaim University Faculty of Sports Sciences. The study consisted of two stages. On the first day of the visit ([Figure 2](#)), the participants' height (Tarti Telescopic Height Meter) and weight (Tanita MC 780 ST Black) measurements were determined. In the next stage, before the supplementation period, resting venous blood samples of the participants were taken from the antecubital vein by a specialist nurse working at Istanbul Sabahattin Zaim University Health Unit. Following the

blood collection process, the randomization processes of the participants were carried out. For this purpose, written numbers from 1 to 24 were placed inside a box in a way that the participants could not see, and the participants were asked to choose one of the numbers at random, accompanied by an independent observer other than the researcher. This process was recorded by the observer both on the survey form and digitally. The second day of the visit took place after a 21-day reinforcement period ([Figure 2](#)), blood samples were collected from the participants by a healthcare professional at rest, 2 h, 24 h, 48 h and 72 h after exercise, and were centrifuged by the researcher and stored at -20 degrees.

[figure not shown]

Figure 2. Experimental Design Scheme for conducting the study

High-Intensity Interval Training Protocol

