Muscle pain sensation in the leg extensor and leg flexor muscles was determined using the Numbered Pain Rating Scale (NPRS), one of the most widely used scales due to its simplicity and practicality [38-40]. The NPRS is a scoring method where a score of zero represents no pain and a score of 10 represents maximum pain. While the NPRS has been validated on numerous patients as a measurement tool for pain intensity [41], its use as a screening tool has not yet been tested [41]. In the application, the patient is asked to rate the severity of their pain. This score is used as the pain score. In this study, we classified the scale scores as mild (1-3), moderate (4-6), or severe (7-10) as previously described [39,42]. Following 21 days of supplementation, participants were asked to quantify their pain sensations using the NPRS

during blood sample collection at 2, 24, 48, and 72 hours after the HIIT protocol. Feedback from participants was recorded on the questionnaire by the supervisor.

Blood Sampling and Analysis

Total carnitine blood sample was collected from the antecubital vein at rest before the 21-day LC supplementation period by a specialist nurse at Istanbul Sabahattin Zaim University Health Unit, as well as immediately before HIIT and at 2 hours, 24 hours, 48 hours and 72 hours after HIIT following the 21 days of supplementation (CK,LDH,). The collected blood samples were kept at room temperature for approximately 30 minutes and then centrifuged at +4°C, 3000 rpm, for 20 minutes using a centrifugal machine (Hitachi Koki Himac CR22N High-Speed Refrigerated Centrifuge, cCS Aus model/913350C2). After the centrifugation process, the transparent liquid remaining in the tube was transferred to 2 ml Eppendorf tubes, then stored at -20 C and analyzed in the laboratory. In addition, following 21 days of supplementation period, blood lactate levels were determined from the fingertip immediately before the HIIT test and at the 1st, 3rd, 5th, 7th, 9th and 11th minutes after the end of the test.

Human Total Carnitine Measurement from Serum

Total carnitine levels in serum samples were measured using a Human Total Carnitine ELISA kit (Bioassay Technology Laboratory, Shanghai, China). Absorbance readings were obtained with a Chromate 4300 microplate reader (Awareness Technology, Inc., [name]). Results were expressed in nmol/ml. Data were calculated using linear regression, with absorbance measured at 450 nm.

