Measurement of CRP, CK, LDH and Uric Acid

Serum CK and LDH were analyzed on a fully automatic analyzer (Roche Cobas Integra 400 Plus, Roche Diagnostics GmbH, Mannheim, Germany) using ROCHE kits (Mannheim, Germany).

Statistical Data Analysis

Data obtained using a double-blind placebo control group experimental design was analyzed using SPSS 25.0 statistical software. The analysis process began by assessing whether the data exhibited a normal distribution. Normality of the data was assessed using the Shapiro–Wilk test, as well as skewness and kurtosis values. Homogeneity of variances was examined using Levene’s test. A two-way repeated measures ANOVA (condition × time) was performed to

determine the effects of L-Carnitine (LC) and placebo (PLS) supplementation on BMI, body fat percentage, lean body mass, resting heart rate, blood lactate concentration, delayed onset muscle soreness (DOMS), and muscle damage markers (CK, LDH) across different time points. When significant main or interaction effects were found, pairwise comparisons were conducted using the Bonferroni post-hoc test. All data are presented as mean \pm standard deviation (SD). Statistical significance was accepted at $p < 0.05$.

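### The repeated measures ANOVA needs a complete set of time points and the visible text gives no alternative, so any missed draw or score would cost precision and, if loss differs by arm, could shrink the treatment difference

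*Combined protocol and SAP*

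**What the plan says.** The Statistical Data Analysis section reports that the data "was analyzed using SPSS 25.0 statistical software". The outcome method is given in one sentence, "A two-way repeated measures ANOVA (condition × time) was performed to" assess the two supplements on a list that includes blood lactate, "delayed onset muscle soreness (DOMS), and muscle damage markers (CK, LDH) across different time points". Bonferroni pairwise comparisons follow any significant effect. "Statistical significance was accepted at" p < 0.05.

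The values needed from each participant after supplementation are:
- **CK and LDH:** five draws, "immediately before HIIT and at 2 hours, 24 hours, 48 hours and 72 hours after HIIT" (Blood Sampling and Analysis). The study procedures under METHOD agree: "blood samples were collected from the participants by a healthcare professional at rest, 2 h, 24 h, 48 h and 72 h after exercise".
- **Soreness:** four scores, taken "during blood sample collection at 2, 24, 48, and 72 hours after the HIIT protocol" (Determination of Muscle Pain Sensation).
- **Lactate:** seven fingertip samples, one just before the test and six up to minute 11 after it (Blood Sampling and Analysis).

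The visible text has no missing-data rule, imputation, mixed model, analysis set or sensitivity analysis. It does not name the SPSS procedure and does not mention deleting incomplete cases. It reports no missed draw or score. The text under the Participants heading is not in the copy reviewed, so participant flow may be described there.

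**The concern.** A standard repeated measures ANOVA works on one complete row per participant for each outcome. Someone with pre-exercise, 2, 24 and 48 h values who misses 72 h drops out of every time point of that outcome, including those at which they were measured. Soreness is scored at the blood draw, so one missed visit after exercise would remove the participant from the soreness, CK and LDH analyses together. This holds however the condition factor is structured.

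Two things are at stake. The first is precision, because whole participants are lost for single missing values. The second is the comparison itself. The analysed set becomes those who attended every visit, which is a selection made after randomisation. If attendance depends on soreness and the supplement changes soreness, the two arms are selected differently.

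**Working it through.** The plan states no dropout rate, power, effect size or correlation, so there is no figure of its own to reproduce. The rates, effects and correlation below are assumptions.

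**Inputs from the documents.** k = 4 time points for soreness and 5 for CK/LDH. The number of participants is unclear: the header gives "Actual Enrollment: 205 participants", while the randomisation draw under METHOD used numbers 1 to 24.

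**1. Participants lost.** If each visit is missed independently with probability q, the share deleted is 1 − (1 − q)^k.

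| q | Soreness, k = 4 | CK/LDH, k = 5 |
|---|---|---|
| 1% | 3.9% | 4.9% |
| 2% | 7.8% | 9.6% |
| 5% | 18.5% | 22.6% |
| 10% | 34.4% | 41.0% |

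At q = 5%, CK/LDH keeps 0.95^5 = 0.774 of participants: 24 × 0.774 = 18.6, or 205 × 0.774 = 158.6. Independence makes these figures high; misses clustered in the same people would lower them.

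**2. Power.** Normal approximation, two-sided 0.05 (the documents do not state sidedness), one comparison of two means: Φ(d√(n/2) − 1.96), with n multiplied by 0.774 for complete cases.
- 12 per arm, d = 1 SD: 0.69 falls to 0.58.
- 102 per arm, d = 0.5 SD: 0.95 falls to 0.88.

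**3. Bias when loss depends on soreness.** Assume four visits with SD 1 and correlation 0.6, and a true difference of 0.5 SD at each. The 72 h visit is missed with probability 50% if the 48 h score exceeds the placebo mean by more than 0.8 SD, and 5% otherwise. In units of each arm's own mean the threshold t is 0.8 for placebo and 1.3 for L-carnitine.
- Share deleted, 0.05 + 0.45 × P(Z > t). Placebo: 0.05 + 0.45 × 0.212 = 14.5%. L-carnitine: 0.05 + 0.45 × 0.097 = 9.4%.
- Shift in the 48 h mean among those kept, −0.45 φ(t)/(1 − share deleted). Placebo: −0.45 × 0.2897/0.8547 = −0.1525. L-carnitine: −0.45 × 0.1714/0.9064 = −0.0851. The gap is 0.0675.
- Complete-case difference at 2 h and 24 h, where nothing is missing: 0.50 − 0.6 × 0.0675 = 0.46.
- Average over four visits: 0.50 − 0.0675 × (1 + 3 × 0.6)/4 = 0.50 − 0.047 = 0.453. Simulation under the same rule gave 0.451, and using all observed values recovered 0.496 to 0.498.

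**4. Other leaving rules.** Simulated with 200,000 per arm, participants leaving after the 24 h visit. Leaving probability is 50% above the control upper quartile and 5% below it, except in the random row (16.25% for all) and the control-only row (flat 5% in the L-carnitine arm).

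| True difference | Leaving depends on | Complete case | Likelihood |
|---|---|---|---|
| 0.5 | nothing (random) | 0.502 | 0.501 |
| 0.5 | observed 24 h value | 0.449 | 0.500 |
| 1.0 | observed 24 h value | 0.909 | 0.996 |
| 0.5 | unseen 48 h value | 0.453 | 0.490 |
| 0 | observed 24 h value, same rule in both arms | −0.001 | 0.001 |
| 0 | observed 24 h value, control arm only | −0.118 | 0.003 |

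Random loss and equal loss under no effect give no bias. Loss that differs by arm, through a real effect or an arm-specific rule, does.

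**The case against.** The strongest reply is that nothing shows any value was missed. The follow-up lasts 72 h, the procedures say samples were taken at each time, and participant flow may be given under Participants. With complete data nothing is deleted. This stands: a reader might infer that collected data were discarded, and the documents do not support that. Complete-case analysis is itself inferred from the named method, not stated.

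A reader might also infer that the comparison is biased whenever the sorest participants leave. That is too strong. Loss must also differ between arms. Under no effect and a common leaving rule both arms are selected alike, and the bias is zero.

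The illustrated bias is small. For a four-visit average at correlation 0.6, the standard error is √(2/n × 0.7): 0.34 SD at 12 per arm and 0.12 SD at 102 per arm. A shift of 0.05 SD lies well inside either, and it needs a steep assumed rule.

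Deletion is also per outcome: a missing soreness score alone leaves CK and LDH intact. No loss rate is given for lactate, because its seven samples come from one short session and cannot be treated as independent chances of loss.

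What survives is that the method depends on completeness, the visible text does not say what happens without it, and a better analysis is available in the same software.

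**Conclusion.** The point holds as a conditional weakness of the analysis method. If any draw or score is missing, the standard repeated measures ANOVA discards that participant's remaining values for the outcome.

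The size depends on rates the documents do not give. Over an assumed 1% to 10% missed independently per visit, 3.9% to 34.4% of participants are lost for soreness and 4.9% to 41.0% for CK/LDH. Attenuation of about 0.05 SD from a true 0.50 SD requires loss that depends on soreness and differs by arm. The documents do not establish that data were lost or that the reported comparison is biased. With 24 or 205 participants both appearing in the text, the practical loss cannot be fixed.

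**What to change.** Analyse CK, LDH, soreness and lactate with a likelihood-based linear mixed model for repeated measures, with arm, time and arm × time as fixed effects. Include every randomised participant with any value after exercise, in the arm drawn. Report the number contributing by arm, outcome and time; if no values are missing, that table shows it.

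The number randomised may be as small as 24. An unstructured covariance has k(k + 1)/2 parameters: 10 for soreness, 15 for CK/LDH and 28 for lactate. If it cannot be estimated, use a more parsimonious structure such as compound symmetry. Apply a small-sample degrees-of-freedom correction in either case.

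The cost is a reanalysis in the same software and a few lines of text. The downside is the missing-at-random assumption. If leaving depends on unseen values, the model reduces the bias without removing it (0.490 against 0.453 for a true 0.50), so add a sensitivity analysis if values are missing. Participants who left before exercise remain outside the model and should be counted by arm. The study was completed on June 5, 2025, so changes to data collection are no longer possible.

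### For CK, LDH and lactate, neither planned omnibus ANOVA test estimates the average post-exercise LC-placebo difference; a baseline-adjusted contrast would, at little cost

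*Combined protocol and SAP*

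**What the plan says.** The study header gives "Intervention Model: Parallel Assignment", and the Supplementation Protocol describes one group taking LC and another taking placebo capsules. Under Statistical Data Analysis, "A two-way repeated measures ANOVA (condition × time) was performed to" determine the supplement effects on body composition, resting heart rate, lactate, soreness, CK and LDH. The follow-up rule is: "When significant main or interaction effects were found, pairwise comparisons were conducted using the Bonferroni post-hoc test". The significance level is 0.05. The section does not say whether condition is between- or within-subject. It names no primary contrast or time point, and states no baseline adjustment, sphericity correction or handling of missing samples.

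The sampling schedule differs by outcome:

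- **CK and LDH:** "immediately before HIIT and at 2 hours, 24 hours, 48 hours and 72 hours after HIIT following the 21 days of supplementation" (Blood Sampling and Analysis), so one pre-exercise and four post-exercise values.
- **Lactate:** immediately before the test and at 1, 3, 5, 7, 9 and 11 minutes after it, so one pre-exercise and six post-exercise values.
- **Soreness (NPRS):** "during blood sample collection at 2, 24, 48, and 72 hours after the HIIT protocol" (Determination of Muscle Pain Sensation), so four post-exercise values and no pre-exercise score.

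**The concern.** The trial asks whether LC changes muscle damage and soreness after high-intensity exercise. For CK, LDH and lactate, an effect on the response to exercise cannot be present in the pre-exercise sample. The planned model nevertheless treats that sample as one more level of time. This has two consequences. The condition main effect is diluted by a time point at which no such effect is expected. The information in the pre-exercise value about an athlete's later values is also not used to reduce error. The interaction does use divergence from rest, but it spreads the question over several degrees of freedom and returns a p-value without a direction or a size.

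At stake are power for the blood markers and the lack of a single defined treatment estimate with a confidence interval. The Bonferroni comparisons do not fill the gap. They depend on a significant omnibus result, and the plan does not say which comparisons form the family.

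**Working it through.** The documents give no power, SD, correlation or effect size, so there is no stated figure to reproduce.

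**Inputs from the documents.** Five CK/LDH times, seven lactate times, four soreness times; alpha 0.05; two candidate sizes, 24 ("written numbers from 1 to 24 were placed inside a box") and 205 (enrolment in the study header).

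**Assumptions.** Equal arms (12/12 or 102/103), SD 1 at each time, one common correlation ρ between times, no LC-placebo difference before exercise.

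**Step 1: dilution.** With a constant post-exercise difference d, the main effect estimates

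- CK/LDH: (0 + 4d)/5 = 0.8d
- lactate: (0 + 6d)/7 = 0.86d
- soreness: 4d/4 = d, so no dilution.

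**Step 2: power for CK/LDH.** Let h = n1·n2/(n1+n2), N = n1+n2, and let μ be the vector of LC-placebo differences over the five times, with mean m. Noncentrality parameters:

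- main effect, F(1, N−2): h·m² / [(1+4ρ)/5]
- interaction, F(4, 4(N−2)): h·Σ(μ−m)² / (1−ρ)
- mean of the four post-exercise values adjusted for the pre-exercise value, F(1, N−3), approximate: h·(post-exercise mean difference)² / [(1+3ρ)/4 − ρ²] × (N−4)/(N−3)

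Worked case, N = 24, d = 0.8 at all four post-exercise times, ρ = 0.5, h = 6:

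- main effect: 6 × 0.64² / 0.6 = 4.10, power 0.490
- interaction: 6 × (0.64² + 4 × 0.16²) / 0.5 = 6 × 0.512 / 0.5 = 6.14, power 0.457
- adjusted contrast: 6 × 0.8² / 0.375 × 20/21 = 9.75, power 0.846

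A 20,000-run simulation of this case gave 0.490, 0.461 and 0.844.

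Constant effect, both sizes:

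| N, d | ρ | Main effect | Interaction | Adjusted contrast |
|---|---|---|---|---|
| 24, 0.8 | 0.3 | 0.618 | 0.332 | 0.836 |
| | 0.5 | 0.490 | 0.457 | 0.846 |
| | 0.7 | 0.405 | 0.701 | 0.927 |
| | 0.8 | 0.373 | 0.881 | 0.978 |
| 205, 0.3 | 0.3 | 0.732 | 0.414 | 0.930 |
| | 0.5 | 0.598 | 0.562 | 0.936 |
| | 0.7 | 0.501 | 0.811 | 0.979 |
| | 0.8 | 0.463 | 0.947 | 0.996 |

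The adjusted contrast exceeds the better planned test by 22, 36, 23 and 10 points at N = 24, and by 20, 34, 17 and 5 points at N = 205.

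**Step 3: change the effect shape.** Put the whole difference at 24 h (N = 24, d = 0.8, ρ = 0.5). The post-exercise mean difference is 0.8/4 = 0.2 and the five-time mean is 0.16.

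- main effect: 6 × 0.16² / 0.6 = 0.256, power 0.077
- interaction: Σ(μ−m)² is again 0.512, power 0.457
- adjusted contrast: 6 × 0.2² / 0.375 × 20/21 = 0.61, power 0.116

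The adjusted contrast still beats the main effect, but the interaction is far ahead of both.

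**Step 4: sphericity.** Simulated null, 12 per arm, AR(1) correlation 0.8 (assumed), 20,000 runs: the uncorrected interaction test rejects about 7% of the time with five times and about 9% with seven. With Greenhouse-Geisser correction it rejects about 4.5%.

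**The case against.** A reader might infer that the analysis is wrong for a parallel-group trial because both factors would be within-subject. The documents do not support that. Condition × time is a common label for the mixed ANOVA with condition between athletes. The same section refers to a placebo control group and to Levene's test, both of which suit a between-group comparison, and nothing says that condition was fitted as within-subject. Only its role is left unstated.

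A reader might also infer that no planned test addresses the post-exercise difference for any outcome. That fails for soreness: with four post-exercise scores and no earlier one, the condition main effect is exactly the average LC-placebo difference. For CK and LDH, the interaction does test whether the arms diverge from rest, and the Bonferroni comparisons may include LC against placebo at each time.

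The strongest objection is that the power gain depends on the assumed effect shape. This stands against any claim of general superiority: with a peaked effect, the interaction beats the proposed contrast. It does not rescue the condition main effect, which was weaker than the adjusted contrast in every case computed here.

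The covariate is also open to challenge. The pre-HIIT sample follows 21 days of supplementation, so it is post-randomisation, and adjusting for it changes the question if LC alters resting values. That must be disclosed and tested. The planned interaction, however, already contrasts later values with the same sample.

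Finally, the documents do not say that sphericity was left uncorrected, and they report no missing samples. Those points are precautions, not documented errors.

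**Conclusion.** The point holds for CK, LDH and lactate only. No planned omnibus test estimates the average post-exercise LC-placebo difference. The condition main effect is diluted (to 0.8d for CK/LDH and 0.86d for lactate under a constant effect) and leaves the pre-exercise value unused as a covariate.

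Under a constant effect, replacing that main effect with a baseline-adjusted contrast adds about 22 to 60 points of power in the N = 24 cases and 20 to 53 points in the N = 205 cases. These figures rest on assumed SD, correlation, effect shape and effect size, none of which the documents give. Sample size is not settled either, since 24 allocation numbers and 205 enrolled are not reconciled. The direction of the comparison with the main effect is the same at both sizes. The comparison with the interaction depends on effect shape, so the interaction should be kept.

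This is a cheap improvement that should be made. It does not show that the planned analysis is invalid.

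**What to change.** 1. State that condition is a between-subject factor and time a within-subject factor.
2. For CK, LDH and lactate, fit a linear mixed model to the post-exercise values with arm, time, arm × time and the pre-HIIT value as covariate, using all available samples and small-sample degrees of freedom.
3. Report the adjusted LC-placebo difference averaged over the post-exercise times, with a 95% CI. Keep the arm × time test and the per-time differences as supportive, because they are more sensitive to an effect that peaks or fades.
4. Add a sensitivity analysis without the pre-HIIT covariate, or with the pre-supplementation CK/LDH value if it was measured; the text leaves that unclear.
5. If the ANOVA is kept, state a Greenhouse-Geisser correction.
6. Soreness needs no change on this point: its condition main effect already is the average post-exercise difference.

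The cost is a few sentences in the analysis section and one model per outcome, which the MIXED procedure in the SPSS version already named can fit. No new data are needed. The header dates show that the study is complete, so if the ANOVA has already been run, the new model should be reported as a disclosed re-analysis beside it. The remaining downside is the post-supplementation covariate, which item 4 addresses.

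### Eight outcomes are each tested at 0.05 with no control across them, and the post-hoc rule neither ties L-carnitine versus placebo comparisons to an arm-related effect nor defines its Bonferroni family

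*Combined protocol and SAP*

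**What the plan says.** The Statistical Data Analysis section describes a single model for every outcome: "A two-way repeated measures ANOVA (condition × time) was performed to" assess L-carnitine (LC) against placebo (PLS). The outcomes are BMI, body fat percentage and lean body mass, followed by "resting heart rate, blood lactate concentration, delayed onset muscle soreness (DOMS), and muscle damage markers (CK, LDH) across different time points". That makes eight. The threshold is common to all of them: "Statistical significance was accepted at $p < 0.05". No outcome is ranked above another in that section, and no adjustment across outcomes is described.

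The follow-up rule is: "When significant main or interaction effects were found, pairwise comparisons were conducted using the Bonferroni post-hoc test". It does not say which comparisons a given effect opens. Nor does it say whether Bonferroni is applied to the two arms within a time point, to the time points, or to all arm-by-time cells.

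The opening of the Method section gives a narrower purpose: "to investigate the effects of L-carnitine supplementation on markers of muscle damage and delayed onset muscle soreness". Three of the eight outcomes (CK, LDH, DOMS) fall within it. On sampling, it states that "blood samples were collected from the participants by a healthcare professional at rest, 2 h, 24 h, 48 h and 72 h after exercise". The section on muscle pain gives four NPRS ratings, and the blood sampling section gives seven lactate readings.

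**The concern.** There are two separate problems.

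**Across outcomes.** A two-way ANOVA gives two results per outcome that bear on L-carnitine: the condition effect and the condition-by-time interaction. With eight outcomes at 0.05 each and no stated order, a favourable result on any of them can be presented as an effect of the supplement. The 5% level then describes each test but not the trial's conclusion.

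**Within an outcome.** Time is a main effect. After exercise to exhaustion, CK, LDH, soreness and lactate should change over time whether or not L-carnitine does anything. As worded, that change is enough to open pairwise comparisons, and nothing excludes LC versus PLS at each time point. With two arms there is only one such comparison per time point, so a Bonferroni family confined to a single time point would divide by one and correct nothing. Whether error is controlled within an outcome therefore depends on a definition that the plan does not give.

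**Working it through.** The plan states no family-wise error rate, so there is no figure of its own to reproduce.

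**Inputs from the document.** Level 0.05 per test; eight outcomes; three of them in the stated aim; five time points for CK and LDH, four for DOMS, seven for lactate.

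**Assumed inputs.** 12 per arm: the randomisation paragraph uses numbers 1 to 24, while the front page gives an enrolment of 205; sample size has almost no effect on a type I error rate. Two time points for BMI, body fat, lean mass and heart rate. Correlations as shown.

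**Step 1. One L-carnitine test per outcome.** Under independence the chance of at least one false positive in k tests is 1 - 0.95^k.

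- Eight outcomes: 1 - 0.95^8 = 33.7%.
- CK, LDH and DOMS: 1 - 0.95^3 = 14.3%.

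With equally correlated normal test statistics (400,000 draws):

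| Correlation | Eight outcomes | Three outcomes |
|---|---|---|
| 0.3 | 29.9% | 13.7% |
| 0.5 | 25.0% | 12.5% |
| 0.8 | 15.8% | 9.9% |

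A second simulation (20,000 runs, 12 per arm) gave 29.7% and 26.3% for eight outcomes at 0.3 and 0.5.

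**Step 2. Condition and interaction both counted.** Sixteen independent tests give 1 - 0.95^16 = 56.0%. A null simulation of the ANOVA (4,000 runs per setting, within-person correlation 0.5) gave 57%, 54%, 51% and 47% at outcome correlations of 0, 0.3, 0.5 and 0.8. For CK, LDH and DOMS alone the range was 22-28%. Outcome correlation was placed on subject effects only, so the interaction tests stayed independent across outcomes. If those were correlated too, the figures would be lower.

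**Step 3. Arm comparisons at each time point, one outcome with five time points (CK or LDH).**

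- No correction across time: 1 - 0.95^5 = 22.6% under independence; simulated 21.0%, 19.1% and 14.9% at within-person correlation 0.3, 0.5 and 0.7.
- Bonferroni across the five: each test at 0.05/5 = 0.01, so the error is at most 5 x 0.01 = 5% under any correlation.

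**Step 4. Step 3 carried over CK, LDH and DOMS**, with the comparisons always open because a time effect is expected: 38-46% without correction across time, and 10-12% with Bonferroni across time points. The second range is what three outcomes at no more than 5% each would produce (compare 14.3% in step 1). The open entry rule adds nothing beyond step 1 when Bonferroni spans the time points, and a good deal when it does not.

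**Step 5. After the change.** Holm over three outcomes compares the smallest p-value with 0.05/3 = 0.0167, the next with 0.05/2 = 0.025 and the last with 0.05. The family-wise error over the three is then at most 5% under any correlation.

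**The case against.** A reader might infer that the post-hoc rule makes the chance of a false L-carnitine claim one in three or more. The documents do not support that. The 33.7% comes entirely from eight independent tests and owes nothing to the post-hoc rule. It is the top of the one-test-per-outcome range, because BMI, body fat and lean mass plausibly move together, as do CK and LDH. Figures above it require condition and interaction both to count as evidence, or Bonferroni not to span the time points. The plan settles neither.

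Four further points have force.

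- The usual follow-up to a time effect is a comparison between times, and the plan nowhere says that a time effect triggers arm comparisons. So the rule is ambiguous rather than plainly wrong; it still needs to exclude the other reading.
- The stated aim covers three outcomes, so 14% is the fairer figure for a false claim on that aim. But the analysis section gives the other five the same test and threshold, and nothing prevents a claim from them.
- The absence of a primary outcome can be confirmed only for the text available. If one was named under Participants, the analysis section still gives it no special role.
- The heading "Measurement of CRP, CK, LDH and Uric Acid" might suggest an outcome list left open. This is weak evidence: the paragraph beneath it covers only CK and LDH, so the heading may simply be a leftover. Total carnitine, which is measured but not in the analysis list, is the clearer gap, though a small one.

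**Conclusion.** The concern holds in this form. No multiplicity control across the eight outcomes is described. With one L-carnitine test each, the chance of at least one false finding is up to about 34% under independence, about 16-30% at assumed correlations of 0.8-0.3, and about 14% or less on the stated aim. If condition and interaction both count, it is about 47-57% over the eight, subject to the simulation assumptions above. All these figures take L-carnitine to have no effect on any outcome considered.

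The post-hoc rule is a distinct defect of definition. Its cost is about 15-21% per outcome for CK or LDH if arm comparisons are uncorrected across time (within-person correlation 0.7-0.3), and at most 5% if Bonferroni spans the time points. The arithmetic is secure; which reading was actually applied cannot be determined from the text.

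**What to change.** 1. Use one arm-related test per outcome, either the condition-by-time interaction or the overall post-exercise arm contrast, and state which. If results by arm have already been seen, say that the choice came afterwards.
2. Apply Holm across CK, LDH and NPRS soreness. The front page gives completion on June 5, 2025 and the analysis is written in the past tense, so selecting a single primary now would be a choice made after the data.
3. Label BMI, body fat, lean mass, resting heart rate and lactate as exploratory, with no efficacy claim.
4. Let a time main effect open only comparisons between times.
5. Let LC versus PLS comparisons follow only the test in item 1, with Bonferroni across all time points of that outcome: 0.05/5 = 0.01 for CK and LDH, and 0.05/4 = 0.0125 for DOMS.

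No new data are needed. The cost is re-analysis or relabelling of existing results and a stricter threshold for each claim, so a finding that rests on an unadjusted p-value just under 0.05 may no longer stand.
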